2.12 Interim analysis

Commercially Confidential Information

3 Sample size calculation

3.1 Primary endpoint(s)

Commercially Confidential Information

At final analysis, MBL949 arms 1, 2, and 3 (if not terminated early) will each have 12 participants, and the placebo arm will have at least 24 participants who complete week 16 weight assessment. Therefore, MBL949 efficacy group will have a sample size of either 24 or 36. Conservatively assuming that the efficacy group and placebo arm each has 24 participants, the power for efficacy criteria is still 95%.

At final analysis, if MBL949 arm 4 has been triggered and completed, the weight change of this arm will be compared to MBL949 efficacy group.

Commercially Confidential Information

Weight change in MBL949 arm 4 will be compared against placebo arm and MBL949 efficacy group, respectively. Assuming that the true weight change in MBL949 arm 4 is -2kg, there is at least 77% probability of declaring MBL949 arm 4 having more weight loss than placebo, and at least a 99% probability of declaring MBL949 efficacy group having more weight loss than MBL949 arm 4, given sample sizes of 12, ≥ 24 , and ≥ 24 in MBL949 arm 4, MBL949 efficacy group, and placebo arm, respectively, where type I error rate is 0.1.

Commercially Confidential Information

4 Change to protocol specified analyses

No change from protocol specified analysis was made.

5 Appendix

5.1 Imputation rules

N/A

5.1.1 Study drug

No imputation will be made to the start date and end date of study treatment.

5.1.2 AE date imputation

5.1.2.1 AE start date imputation

The following table explains the notation used in the logic matrix. Please note that missing start dates will not be imputed.

	Day	Month	Year
Partial Adverse Event Start Date	Not used	MON	YYYY
Treatment Start Date	Not used	TRTM	TRTY

The following matrix explains the logic behind the imputation.

	MON MISSING	MON < TRTM	MON = TRTM	MON > TRTM
YYYY MISSING	(1) No convention	(1) No convention	(1) No convention	(1) No convention
YYYY < TRTY	(2.a) Before Treatment Start	(2.b) Before Treatment Start	(2.b) Before Treatment Start	(2.b) Before Treatment Start
YYYY = TRTY	(4.a) Uncertain	(4.b) Before Treatment Start	(4.c) Uncertain	(4.c) After Treatment Start
YYYY > TRTY	(3.a) After Treatment Start	(3.b) After Treatment Start	(3.b) After Treatment Start	(3.b) After Treatment Start

Impute AE start date -

1. If the AE start date year value is missing, the date uncertainty is too high to impute a rational date. Therefore, if the AE year value is missing, the imputed AE start date is set to NULL.
2. If the AE start date year value is less than the treatment start date year value, the AE started before treatment. Therefore:
 - a. If AE month is missing, the imputed AE start date is set to the mid-year point (01JulYYYY).
 - b. Else if AE month is not missing, the imputed AE start date is set to the mid-month point (15MONYYYY).
3. If the AE start date year value is greater than the treatment start date year value, the AE started after treatment. Therefore:
 - a. If the AE month is missing, the imputed AE start date is set to the year start point (01JanYYYY).
 - b. Else if the AE month is not missing, the imputed AE start date is set to the later of (month start point (01MONYYYY), treatment start date + 1 day).
4. If the AE start date year value is equal to the treatment start date year value:
 - a. And the AE month is missing the imputed AE start date is set to the treatment start date + 1 day.
 - b. Else if the AE month is less than the treatment start month, the imputed AE start date is set to the mid-month point (15MONYYYY).
 - c. Else if the AE month is equal to the treatment start date month or greater than the treatment start date month, the imputed AE start date is set to the later of (month start point (01MONYYYY), treatment start date + 1 day).

If AE end date is available and the imputed AE start date is greater than the AE end date, then imputed AE start date should be set to the AE end date.

5.1.2.2 AE end date imputation

1. If the AE end date month is missing, the imputed end date should be set to the earliest of the (treatment follow up period date, 31DECYYYY, date of death).
2. If the AE end date day is missing, the imputed end date should be set to the earliest of the (treatment follow up period date, last day of the month, date of death).
3. If AE year is missing or AE is ongoing, the end date will not be imputed.

5.1.3 Concomitant medication date imputation

5.1.3.1 Concomitant medication start date imputation

Rules for imputing the CM start date:

The following table explains the notation used in the logic matrix. Please note that missing start dates will not be imputed.

	Day	Month	Year
Partial CMD Start Date	Not used	MON	YYYY
Treatment Start Date	Not used	TRTM	TRTY

The following matrix explains the logic behind the imputation.

	MON MISSING	MON < TRTM	MON = TRTM	MON > TRTM
YYYY MISSING	(1) Uncertain	(1) Uncertain	(1) Uncertain	(1) Uncertain
YYYY < TRTY	(2.a) Before Treatment Start	(2.b) Before Treatment Start	(2.b) Before Treatment Start	(2.b) Before Treatment Start
YYYY = TRTY	(4.a) Uncertain	(4.b) Before Treatment Start	(4.a) Uncertain	(4.c) After Treatment Start
YYYY > TRTY	(3.a) After Treatment Start	(3.b) After Treatment Start	(3.b) After Treatment Start	(3.b) After Treatment Start

1. If the CM start date year value is missing, the imputed CM start date is set to one day prior to treatment start date.
2. If the CM start date year value is less than the treatment start date year value, the CM started before treatment. Therefore:
 - a. If the CM month is missing, the imputed CM start date is set to the mid-year point (01JulYYYY).
 - b. Else if the CM month is not missing, the imputed CM start date is set to the mid-month point (15MONYYYY).
3. If the CM start date year value is greater than the treatment start date year value, the CM started after treatment. Therefore:

- a. If the CM month is missing, the imputed CM start date is set to the year start point (01JanYYYY).
 - b. Else if the CM month is not missing, the imputed CM start date is set to the month start point (01MONYYYY).
4. If the CM start date year value is equal to the treatment start date year value:
- a. And the CM month is missing or the CM month is equal to the treatment start date month, then the imputed CM start date is set to one day prior treatment start date.
 - b. Else if the CM month is less than the treatment start date month, the imputed CM start date is set to the mid-month point (15MONYYYY).
 - c. Else if the CM month is greater than the treatment start date month, the imputed CM start date is set to the month start point (01MONYYYY).

If complete (imputed) CM end date is available and the imputed CM start date is greater than the (imputed) CM end date, then imputed CM start date should be set to the (imputed) CM end date.

5.1.3.2 Concomitant medication end date imputation

Rules for imputing the CM end date (based on RAP M3):

1. If CM end day is missing and CM month/year are non-missing then impute CM day as the minimum of treatment end date and the last day of the month.
2. If CM end day/month are missing and CM year is non-missing then impute CM day as the minimum of treatment end date and the end of the year (31DECYYYY).
3. If CM day/month/year is missing then use the treatment end date + 1 day as the imputed CM end date.
4. If imputed CM end date is less than the CM start date, use the CM start date as the imputed CM end date.

5.2 AEs coding/grading

N/A

5.3 Laboratory parameters derivations

Clinically notable values for vital signs are as follows:

- Any significant increase or decrease in vital signs beyond inclusion/exclusion criteria:
 - Systolic blood pressure less than 95 mgHg or greater than 155 mgHg
 - Diastolic blood pressure less than 60 mgHg or greater than 95 mgHg
 - Pulse rate less than 56 or greater than 110 bpm

5.4 Statistical models

5.4.1 Analysis supporting primary objective(s)

The weight of each participant at week 16 will be analyzed with a mixed model for repeated measures (MMRM) as described in Section 2.5.2. The model will be fitted using the SAS procedure “PROC MIXED”. Unstructured covariance matrix will be used (TYPE = UN), thus allowing adjustment for correlations between time points within subjects. If not possible, other appropriate covariance structures will be explored.

Adjusted means and the corresponding variance covariance matrix will be estimated. The estimated treatment differences for treatment comparisons will be tabulated along with the associated 80% confidence intervals and two-sided p-value. No adjustment for multiplicity will be made. For calculation of denominator degrees of freedom Kenwood-Rogers method would be used (DDFM=KR).

The mathematical formula of this MMRM is given as follows:

$$\underline{y} = \beta_0 + \beta_1 \text{treatment} + \beta_2 \text{time} + \beta_3 \text{treatment} * \text{time} + \beta_4 \text{baseline} + \beta_5 \text{glycemic} + \beta_6 \text{treatment} * \text{glycemic} + \beta_7 \text{time} * \text{glycemic} + \beta_8 \text{treatment} * \text{time} * \text{glycemic} + \underline{\varepsilon}$$

where,

- \underline{y} is vector of the absolute change from baseline in weight
- β_0 the fixed effect intercept
- $\beta_1, \beta_2, \beta_3,$ and β_5 the vector coefficients of the corresponding parameters and β_4 the coefficient of corresponding parameter.
 - $\beta_5, \beta_6, \beta_7$ and β_8 depends on the parameter level, if glycemic has two levels then $\beta_5, \beta_6, \beta_7$ and β_8
 - If glycemic parameter has one level, $\beta_5, \beta_6, \beta_7$ and β_8 are dropped from the equation
- $\underline{\varepsilon}$ the vector of residuals where $\underline{\varepsilon} \sim N(0, \mathbf{R})$ with \mathbf{R} is a $m \times m$ diagonal covariance matrix.

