4.7 Rationale for Public Health Emergency mitigation

In Commercially Confidential Information the event of a Public Health emergency as declared by Local or Regional authorities i.e., pandemic, epidemic or natural disaster, additional mitigation procedures to ensure participant safety and trial integrity may be implemented. If allowable by a local Health Authority and depending on operational capabilities, phone calls, virtual contacts (e.g. tele consult) or additional visits by OHPs to the participant's home, can replace onsite study visits (in addition to the already planned off-site visits), for the duration of the disruption until it is safe for the participant to visit the site again.

Notification of the Public health emergency should be discussed with Novartis prior to implementation of mitigation procedures and permitted/approved by Local or Regional Health Authorities and Ethics Committees as appropriate.

5 Study Population

The study population will include obese (BMI ≥ 32 kg/m²) men and women between 18 and 60 years of age with or without T2DM. To account for 15% drop out rate, approximately 106 participants are planned to be randomized to achieve 90 total completers. The Investigator must ensure that all participants being considered for the study meet the following eligibility criteria. No additional criteria should be applied by the Investigator, in order that the study population will be representative of all eligible participants. Participant selection is to be established by checking through all eligibility criteria at both screening, baseline, and prior to randomization as applicable. A relevant record (e.g., checklist) of the eligibility criteria must be stored with the source documentation at the site. Deviation from any entry criterion excludes a participant from enrollment into the study.

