2.5.4 Handling of missing values not related to intercurrent event

All participants with a baseline weight and at least one post-baseline weight measurement will be included in the primary efficacy analysis. Commercially Confidential Information

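### Does the word diagonal in the SAP 5.4.1 model legend undo the unstructured covariance planned for the primary weight analysis?

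*SAP*

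**What the plan says.** SAP 5.4.1 opens with the primary efficacy analysis: "The weight of each participant at week 16 will be analyzed with a mixed model for repeated measures (MMRM) as described in Section 2.5.2". It names PROC MIXED and then the covariance option with its reason: "Unstructured covariance matrix will be used (TYPE = UN), thus allowing adjustment for correlations between time points within subjects". The next sentence covers failure of that option: "If not possible, other appropriate covariance structures will be explored". Inference follows: "The estimated treatment differences for treatment comparisons will be tabulated along with the associated 80% confidence intervals and two-sided p-value".

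The section then writes out the model equation. It has fixed effects for treatment, time, baseline and glycemic status with their interactions, plus a residual, and no random effect. In the legend, the response "is vector of the absolute change from baseline in weight", and the residual is normal with mean zero and covariance R, described as an m x m "diagonal covariance matrix". The dimension m is not defined.

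Two other places bear on the consequences. SAP 2.5.4 says: "All participants with a baseline weight and at least one post-baseline weight measurement will be included in the primary efficacy analysis". Protocol section 5 says: "To account for 15% drop out rate, approximately 106 participants are planned to be randomized to achieve 90 total completers". The model text of SAP 2.5.2, to which 5.4.1 refers, is redacted, as is Protocol 12.4.2.

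**The concern.** With no random effect in the equation, R is the only place where correlation between a participant's visits can enter. Under normality, zero covariance is independence. Read literally, the legend describes a model in which repeated weights on one person are unrelated, while a few lines earlier the same section adopts a structure in order to model that relation.

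What would be at stake is the handling of participants without a week-16 weight. They enter the analysis if they have any post-baseline weight, and 15% dropout is planned. Under an unstructured covariance, their earlier weights inform the week-16 estimate. Under independence they do not, and the week-16 contrast rests on those still observed. That biases the contrast if dropout depends on earlier weight change differently in the two arms. If independence were combined with one common variance and the spread of weight change grows over time, the 80% intervals at week 16 would also be too narrow.

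**Working it through.** **1. What each statement implies.** For t visits per participant, TYPE=UN estimates t(t+1)/2 parameters, of which t(t-1)/2 are covariances between visits. Taking 8 biweekly visits as an illustration (the visits in the model are not visible), that is 8 x 9/2 = 36 parameters and 8 x 7/2 = 28 covariances. A literally diagonal R sets all 28 to zero. The two statements are incompatible as written.

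**2. What m could be.**
- If R is the covariance of all residuals stacked over participants, it is block-diagonal: one t x t block per participant, and zeros elsewhere because participants are independent. An unstructured block inside that matrix is exactly what TYPE=UN fits. One missing word reconciles the legend with the text.
- If R is one participant's matrix (m = t), the legend cancels both the option and its stated reason.

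Only the first reading leaves the section coherent.

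**3. Which statement governs the analysis.** The programmer's instruction consists of the procedure, the option and the purpose. All three appear in running text and agree. The word diagonal appears once, in the last line of a legend that restates the same model in symbols.

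**4. Whether the diagonal matrix could enter as the fallback.** The fallback sentence allows other *appropriate* structures and comes directly after the aim of allowing for correlation between time points. Independence would defeat that aim. The legend describes the main model and is not offered as an alternative. The parameter count under TYPE=UN is 36 for 8 visits, 12 x 13/2 = 78 for 12 and 14 x 15/2 = 105 for 14, against about 106 participants (90/0.85 = 105.9, which reproduces the planned total). A fallback is therefore conceivable, but the count alone does not show that the unstructured fit would fail, and it does not lead to a diagonal R.

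**5. Size if the legend were coded literally.** The documents give no standard deviation or correlation, so these inputs are assumed.
- *Coverage*, with complete data, 8 equally spaced visits, standard deviation linear in time and one common variance: width ratio = sqrt(mean of SD_t^2)/SD_16, and coverage = 2*Phi(1.2816 x ratio) - 1. If the week-2 SD is half the week-16 SD, the ratio is 0.768 and coverage is 2*Phi(0.984) - 1 = 0.675. If the SD is constant, the ratio is 1 and coverage is 0.80. With a separate variance per visit and complete data, the week-16 result is unchanged. The legend does not say the variances are equal.
- *Bias*, simulated with week-16 SD 3 kg, week-2 SD 1.5 kg, adjacent-visit correlation 0.9, 28 v 28 randomized and about 15% dropout: roughly 0.13 to 0.36 kg under independence if dropout depends on earlier weight change in the active arm only, up to 0.61 kg if the dependence is opposite in the two arms, and about 0 if it is the same in both. Under TYPE=UN it stays within about 0.03 kg of zero throughout. The simulation compared two groups without the baseline and glycemic terms of the SAP model.

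**The case for a change.** The strongest case for a change is that this is the primary model and the contradiction is fully visible. No redacted sentence could make a diagonal matrix unstructured. An independent programmer validating the analysis works from the same section, m is undefined, and the word block has to be supplied by the reader. Since the fallback names no structure and no order, the diagonal R is also the only other structure written there. The correction costs a few words.

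Part of this stands. The text is inconsistent, and a literal reading would be a worse analysis wherever week-16 weights are missing. It does not show that the analysis as instructed is at risk. A validating programmer also has TYPE=UN in front of them, with its reason. The fallback argument ties the legend to a sentence that does not mention it and whose context excludes independence. Naming an ordered list of fallback structures is a separate refinement, and a statistician would choose a correlated structure there without being told. How far participants without a week-16 weight depend on the model alone is also unknown, because most of the missing-data, intercurrent-event and sensitivity text is redacted.

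**Conclusion.** This is a clerical slip: almost certainly block-diagonal was meant. With TYPE=UN run as SAP 5.4.1 directs, its effect on the week-16 estimate, the 80% interval and the p-value is nil. The bias and coverage figures apply only if an analyst sets aside the named option and codes the legend, and the coverage loss also needs a common variance. They illustrate a reading that the section itself contradicts and are not an expected error of this trial. The conclusion assumes that the redacted model text in SAP 2.5.2 is consistent with the visible instruction. The word can be corrected whenever the SAP is next revised, but the analysis does not depend on it and the plan needs no change on this account.

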12.8 Sample size calculation

12.8.1 Primary endpoint(s)

Commercially Confidential Information

At final analysis, MBL949 arms 1, 2, and 3 (if not terminated early) will each have 12 participants, and the placebo arm will have at least 24 participants who complete week 16 weight assessment. Therefore, MBL949 efficacy group will have a sample size of either 24 or 36. Conservatively assuming that the efficacy group and placebo arm each has 24 participants, the power for efficacy criteria is still 95%.

At final analysis, if MBL949 arm 5 has been triggered and completed, the weight change of this arm will be compared to MBL949 efficacy group.

Commercially Confidential Information

Weight change in MBL949 arm 4 will be compared against placebo arm and MBL949 efficacy group, respectively. Assuming that the true weight change in MBL949 arm 4 is -2kg, there is at least a 77% probability of declaring MBL949 arm 4 having more weight loss than placebo, and at least a 99% probability of declaring MBL949 efficacy group having more weight loss than MBL949 arm 4, given sample sizes of 12, ≥ 24 , and ≥ 24 in MBL949 arm 4, MBL949 efficacy group, and placebo arm, respectively, where type I error rate is 0.1.

Commercially Confidential Information

13 Ethical considerations and administrative procedures

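### Do the 80% confidence interval and the two-sided p-value conflict with the type I error rate of 0.1 used in the power calculation?

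*SAP*

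**What the plan says.** SAP 5.4.1 fits a mixed model for repeated measures to change in weight, with Kenward-Roger degrees of freedom. The estimated treatment differences "will be tabulated along with the associated 80% confidence intervals and two-sided p-value", without multiplicity adjustment. It names no cut-off for the p-value.

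SAP 3.1 gives the operating characteristics. Its premise reads "Assuming that the true weight change in MBL949 arm 4 is -2kg". The result drawn from this premise is that "there is at least 77% probability of declaring MBL949 arm 4 having more weight loss than placebo". That figure holds "given sample sizes of 12, ≥ 24 , and ≥ 24 in MBL949 arm 4" and the two other groups, and for a calculation "where type I error rate is 0.1". Protocol 12.8.1 has the same figure and the same error rate. The claim is directional in both documents: the event being powered is "declaring MBL949 arm 4 having more weight loss than placebo". For the pooled efficacy group against placebo at 24 each, SAP 3.1 adds that "the power for efficacy criteria is still 95"%.

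The visible text does not say whether 0.1 is one-sided or two-sided. Protocol 12.4.2, whose title covers model, hypothesis and method, is redacted in full. The opening of the weight part of SAP 2.5.2 is redacted, and so is text around the power statements in SAP 3.1 and Protocol 12.8.1. The definition of the efficacy criteria is therefore not visible either.

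**The concern.** A reader who sees 0.1 in the sample size section and a two-sided p-value in the analysis section will tend to put them together and judge p against 0.1. That is a one-sided 0.05 test, whose matching interval is 90%. The SAP prints an 80% interval, whose matching two-sided level is 0.20. It then seems that the interval can exclude zero while the p-value fails.

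If that were so, the 77% would belong to only one of two competing rules, and the choice between them could be made after the data are seen. This would matter here because the study is open-label to the sponsor, the statistician may access the randomization list at any time (Protocol 6.4), and no multiplicity adjustment adds any protection.

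**Working it through.** **Inputs.** Error rate 0.1, directional claim, 12 in arm 4 and 24 on placebo, true change in arm 4 of -2 kg, power at least 77% (SAP 3.1, Protocol 12.8.1). 80% interval and two-sided p-value from one model (SAP 5.4.1). Not visible: the SD and the placebo change. I assume a placebo change of 0 kg, so the difference is 2 kg, and solve for the SD.

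**Step 1: the plan's 77%.** Power = Φ(Δ / (σ√(1/12 + 1/24)) − z), with √(1/12 + 1/24) = √0.125 = 0.3536.

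- One-sided 0.1, z = 1.2816: σ = 2.80 kg gives 2/(2.80 × 0.3536) = 2.020, and 2.020 − 1.282 = 0.739, so Φ = 77.0%.
- Two-sided 0.1, z = 1.6449: σ = 2.373 kg gives 2/(2.373 × 0.3536) = 2.384, and 2.384 − 1.645 = 0.739, so Φ = 77.0%.

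The noncentral t with 34 degrees of freedom gives 2.77 and 2.33 kg. Over σ from 2.3 to 4.0 kg, power (normal) runs from 88.1% to 55.3% one-sided and from 79.2% to 40.9% two-sided. With the SD hidden, the 77% cannot be confirmed, and it does not settle the sidedness.

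**Step 2: are the interval and the p-value different tests?** Let d be the estimated difference (MBL949 minus placebo), s its standard error and ν its degrees of freedom. The upper 80% limit is d + t(0.90, ν) × s. It is below zero when d/s < −t(0.90, ν). That is the condition for a one-sided p < 0.10, and also for a two-sided p < 0.20 with d negative. The interval and the p-value use the same d, s and ν, so this is an identity for any ν, including a Kenward-Roger value.

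| Rule | Normal cut-off | t cut-off, 34 df |
|---|---|---|
| One-sided p < 0.10 | 1.2816 | 1.3070 |
| 80% interval wholly below 0 | 1.2816 | 1.3070 |
| Two-sided p < 0.20, favourable | 1.2816 | 1.3070 |
| Two-sided p < 0.10, favourable (90% interval) | 1.6449 | 1.6909 |

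**Step 3: simulation.** 400,000 trials for each effect, 12 against 24, 34 degrees of freedom, SD 2.8 kg.

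| Rule | Declared, true difference 0 | Declared, true difference -2 kg | Disagrees with 80% interval (0 / -2 kg) |
|---|---|---|---|
| One-sided p < 0.10 | 9.97% | 76.3% | 0 / 0 |
| 80% interval wholly below 0 | 9.97% | 76.3% | not applicable |
| Two-sided p < 0.20, favourable | 9.97% | 76.3% | 0 / 0 |
| Two-sided p < 0.10, favourable | 5.0% | 63.0% | 5.0% / 13.3% |

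The first three rows give the stated 0.1 as a directional error rate.

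**Step 4: where the apparent conflict comes from.** It is all in the last row. In the normal formula, 2.020 − 1.645 = 0.376, so power would be 64.6% instead of 77.0%. This loss depends only on the ratio of the difference to its standard error, which the 77% fixes. A non-zero placebo change would alter the implied SD but not the loss. What the loss does need is the rule itself, that the two-sided p-value is held against 0.1. Neither document states that rule in its visible text.

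**The case for a change.** The strongest opposing case is that 0.1 is the only error rate in view and the only p-value is two-sided, so a report reader will naturally compare the two. On the one-sided reading that reader applies a stricter test than the one powered. On a two-sided reading of 0.1 the matching interval would be 90%, and an 80% interval used as the test would run at two-sided 0.20. On neither reading does the printed p-value, held against the printed 0.1, match the 80% interval.

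Two parts of this stand. The visible text does not call the 0.1 one-sided, and a few words saying so would help a reader. It is also true that a two-sided 0.1 would pair with a 90% interval.

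The rest does not follow. The powered statements are directional and the chosen interval is 80%; both point to one-sided 0.1, and nothing visible points to two-sided. On that reading a two-sided p-value loses no information: when the difference favours MBL949, half of it is the one-sided p-value. The sections that would state the hypothesis and the declaration rule are redacted, so the lack of a visible rule cannot be counted as a gap in the plan or as freedom for the sponsor to choose between outputs.

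**Conclusion.** The concern does not hold. The 80% interval, the two-sided p-value and a directional test at 0.1 are one test on three scales, with a common cut-off of 1.2816 (1.3070 at 34 degrees of freedom) and no disagreement in 400,000 simulated trials per scenario. The 64% power and the 13% and 5% disagreement describe a decision rule that the visible documents do not contain.

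This rests on reading 0.1 as one-sided, which the directional wording and the 80% interval both support, and on the interval and p-value coming from the same model contrast, as SAP 5.4.1 specifies. The 77% itself remains unconfirmed because the SD and placebo change are not visible. Naming the sidedness would be a matter of wording and would change no estimate, interval or conclusion.

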2.5.1 Primary endpoint(s)

Weight

The primary endpoint for efficacy is change-from-baseline in weight at week 16. Baseline weight is defined as the last weight measurement before dosing.

Adverse Events

Primary endpoints for safety and tolerability are occurrences and severities of adverse events.

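### The visible primary MMRM gives baseline weight one slope for all visits; adding baseline-by-time is a cheap improvement that may modestly sharpen the week-16 comparison

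*SAP*

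**What the plan says.** SAP 2.5.1 sets the time point: "The primary endpoint for efficacy is change-from-baseline in weight at week 16". SAP 2.5.4 sets who enters: "All participants with a baseline weight and at least one post-baseline weight measurement will be included in the primary efficacy analysis".

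SAP 5.4.1 introduces its equation with the words "The mathematical formula of this MMRM is given as follows". The response "is vector of the absolute change from baseline in weight". Time is crossed with treatment, with glycemic status and with their product; the glycemic terms are dropped "If glycemic parameter has one level". Baseline appears only as β4·baseline. The legend calls most of the other coefficients vectors, but β4 is "the coefficient of corresponding parameter". So the visible formula has one baseline slope for all visits.

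The same section specifies TYPE = UN, "thus allowing adjustment for correlations between time points within subjects", yet the legend describes R as a "diagonal covariance matrix".

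SAP 5.4.1 refers to SAP 2.5.2 for the model. The model text there is blacked out in the public copy, as is the matching protocol section (12.4.2).

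**The concern.** The outcome is a change from baseline followed from the first days of treatment to week 16. If heavier participants lose more kilograms as treatment goes on, the slope on baseline weight is near zero early and largest at week 16. Under an unstructured covariance, a single slope is a precision-weighted average over visits. Early changes vary little, so they carry most of the weight, and the fitted slope lies near its early value. Baseline weight is then in the model but does little for the week-16 contrast.

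What is at stake is some precision in a trial with active arms of 12. A chance baseline imbalance left in the estimate is this same loss seen in one trial, not a further one.

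**Working it through.** **Plan figures.** Completers (Protocol 3, Enrollment Flow): 5×12 + (12+12+6) = 90, and 90/0.85 = 105.9, so 106 randomized, as stated. The SD is blacked out. The stated 77% for arm 4 (n=12) against placebo (n=24) at −2 kg can be used to back-solve it, assuming no placebo change and one-sided 0.1: 2/(2.8·√(1/12+1/24)) − 1.282 = 0.739, and Φ(0.739) = 77%. That gives SD 2.8 kg. With two-sided 0.1 it is 2.37 kg.

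**Other inputs, all assumed.** Week-16 slope 0.03–0.05 kg/kg; baseline SD 15–20 kg; slope growing linearly or with the square root of time. Table 8-1 schedules 12 post-baseline weights up to week 16 (Days 2, 5, 10, 15, 29, 43, 57, 71, 85, 99, 100, 112). Which of them enter the model is not visible, so the 8 visits from Day 15 without Day 100 are shown as well.

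**Formulas.** With visit covariance S and true slopes b_t, the common slope is b = 1′S⁻¹b_t / 1′S⁻¹1. Let f = b/b₁₆. The week-16 SE relative to a visit-specific slope is √(1 + [(1−f)·b₁₆·SD_base/2.8]²). Here b₁₆·SD_base runs from 0.03×15 = 0.45 kg to 0.05×20 = 1.0 kg.

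**Results at SD 2.8 kg** (measurement error 0.6 kg in the first four rows):

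| Covariance | Slope growth | f, 12 visits | f, 8 visits | SE loss, 12 | SE loss, 8 |
|---|---|---|---|---|---|
| Random walk | linear | 0.035 | 0.163 | 1.2–5.8% | 0.9–4.4% |
| Random walk | square root | 0.163 | 0.396 | 0.9–4.4% | 0.5–2.3% |
| Random slope | linear | 0.015 | 0.038 | 1.2–6.0% | 1.2–5.7% |
| Random slope | square root | 0.227 | 0.345 | 0.8–3.7% | 0.6–2.7% |
| Constant variance, correlation 0.9 | linear | 0.462 | 0.566 | 0.4–1.8% | 0.2–1.2% |
| Constant variance, correlation 0.9 | square root | 0.608 | 0.723 | 0.2–1.0% | 0.1–0.5% |

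In the random-walk case with 12 visits, Days 2, 5, 10 and 15 carry 54%, 28%, 11% and 5% of the weight. An autoregressive structure with rising variance takes f slightly below zero and gives the 7% end.

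**Simulation of the full mean model** (five arms of 12, placebo 30, covariance estimated), which also counts the cost of the extra slopes. With rising variance and a growing slope, f is −5% to 24% with 12 visits and 4% to 41% with 8. The arm 4 versus placebo SE is larger by:
- 0–7% at SD 2.8 kg: 0–1% at slope 0.03 and SD 15, 1–7% at 0.05 and 20;
- 0–11% at 2.0 kg and −1% to 3% at 4.0 kg;
- 0–5% at 2.8 kg with 106 randomized and 15% dropout at random;
- 1–13% at 2.8 kg in an extreme case, rising variance with correlation 0.9 between all visits.

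If the true slope is zero or constant, baseline*time makes the SE 0–1% larger.

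**In kilograms, near the upper end (f = 0).** 2.8·√(1/12+1/30) = 0.956; times √(1+(1.0/2.8)²) = 1.062 gives 1.016. The 80% CI half-widths (×1.282, ignoring the Kenward-Roger degrees of freedom) are about 1.23 and 1.30 kg.

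**Power, one-sided 0.1.** If a stated 95% assumes full adjustment, a 3% larger SE gives (1.645+1.282)/1.03 − 1.282 = 1.56, or 94%. A 6.8% larger SE gives 93%.

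**Bias.** A separate simulation (two groups, 8 visits) gave −0.007 kg (Monte Carlo SE 0.021) with complete data. With the same baseline-dependent dropout in both arms, the two models differed by 0.003 kg (SE 0.004). With baseline-dependent dropout in the active arm only, the common slope gave about 0.03–0.11 kg, against a contrast SE near 0.8 kg.

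**The case against.** A prespecified common slope is a legitimate choice, and nothing in the documents contradicts it. The slope, its growth, the SDs and the covariance are all assumed. At the low end the gain is 0–1%, and if the slope is flat the extra term costs up to 1%. A growing slope is not enough: without rising variance, roughly half or more of the adjustment reaches week 16. SAP 5.4.1 also allows other covariance structures if the unstructured one cannot be fitted. All of this stands, and it is why the point is an optional refinement. Rising variance is nevertheless the natural case for change from baseline under TYPE=UN, and the trade-off favours the term.

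Three stronger readings do not hold:
- A reader might infer that the model is wrong or that the treatment effect is biased. Randomization protects the contrast with complete data. Bias arises only if dropout depends on baseline differently by arm, and it is then small; it reached 0.3 kg or more only when the dependence ran in opposite directions in the two arms.
- A reader might infer that the plan certainly lacks the term. The model text in SAP 2.5.2 is not visible, so only the 5.4.1 formula can be judged.
- A reader might infer from the word diagonal that visits are treated as independent. The explicit PROC MIXED instruction governs the fit, so this is a wording slip and adds no weight to the baseline point.

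**Conclusion.** A cheap improvement, lowest tier, medium confidence. The visible formula is valid. Where the baseline slope grows and the variance of change rises over visits, only part of the baseline adjustment reaches week 16. The SE is then about 0–7% larger than it could be at a residual SD of 2.8 kg, and under 2% larger if variance is constant. The size rests on the assumed slopes, SDs, covariances and visits. The 2.8 kg itself rests on an assumed placebo change of zero and a one-sided test, and whether the planning SD is before or after baseline adjustment is not visible. If it is before, the loss is a gain forgone rather than a shortfall against the stated power.

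**What to change.** Add baseline*time to the primary MMRM in SAP 5.4.1. If SAP 2.5.2 already has it, align the 5.4.1 formula with it.

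As a wording correction only, describe R as block-diagonal with unstructured within-participant blocks, to agree with TYPE=UN.

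Cost: one model term and SAP text, no new data. The term adds up to 11 fixed-effect parameters (7 with 8 visits), and the week-16 SE is up to about 1% larger if baseline weight has no effect or a constant slope. It also removes the small bias under baseline-dependent dropout that differs by arm.
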